### 11.3 Interim analyses and Stopping Rules

We will assess study measures and safety measures in the middle of the study. There are no interim analyses planned that would trigger early stopping for this pilot study as it involves only a single communication with surgeons and a single communication with participating patients. As noted in section 8, above, the discovery of any adverse event would prompt immediate evaluation by the study team (including study statistician and, if necessary, DSMB statistician) to review the events by group to determine whether there

are statistical and/or clinical concerns. The statistician would report their findings to a closed session of the DSMB and/or NIA. Findings would be used to determine what steps would be taken.

## 11.4 Outcomes

### 11.4.1 Primary outcomes

- Percentage of surgeons approached who agree to participate in study (goal: >50%)
- Percentage of patients contacted who agree to participate in study (goal: >50%)
- Surgeon-reported acceptability of intervention (goal: >75% respond “Yes” to question regarding perceived acceptability of nudge intervention)

### 11.4.2 Exploratory outcomes

- Mean pre-post percentage change in procedure-specific prescription size, as measured by OMEs. Mean size of post-intervention prescriptions (from electronic medical record queries) will be compared with mean pre-intervention prescription size by the same surgeon for the same procedure in order to calculate change from baseline.
- Pre-post change in patient opioid consumption, as measured by OMEs
- Pre-post change in satisfaction with overall postoperative analgesia, as measured by patient-reported numeric rating scale
- Pre-post change in patient satisfaction with general amount of opioids prescribed
- Pre-post change in incidence of medical visits for pain (office visits, emergency department visits, and/or hospital admissions)
- Pre-post change in number of subsequent opioid refills after the initial postoperative prescription (from EMR/PDMP data)
- Surgeon-reported perceived usefulness of intervention (goal: median response to question “Do you think the nudge intervention would be useful?”  $\geq 4$  on 0-5 scale, where 0 is “not at all” and 5 “extremely.”)

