## 5 STUDY DESIGN

We plan a pilot randomized controlled trial randomizing surgeons to either intervention (direct feedback) or control (no direct feedback) arms. Surgeons frequently performing specific elective general, gynecologic, orthopedic, and neurological surgeries at VUMC will be identified during a 30-day study lead-in period. Then, patients aged at least 18 years undergoing these surgeries at VUMC during study days 1-60 will be contacted by telephone 14 days postoperatively (study days 15-74) and asked to perform an opioid pill count; they will also be asked about opioid refills, satisfaction with analgesia, emergency room visits or hospitalizations for pain, and opioid misuse. The electronic medical record will be also queried for the size of the initial postoperative opioid prescription as well as evidence of any refills for each enrolled subject. We anticipate successfully contacting 5 patients per day for a total of 300 patients in this initial phase. We plan to consent patients electronically at the time of the telephone contact as consenting patients immediately after surgery may influence their subsequent opioid consumption.

Surgeons will be consented without overt discussion of the nudge intervention. Following the first block of surgeries and associated patient follow-up (study days 1-74), data will be analyzed and then surgeons will be randomized in a 1:1 ratio to the intervention or control arms. Randomization will be stratified by both surgical specialty and by mean opioid prescription size during the initial block of surgeries. After study day 97, surgeons in the intervention arm will be provided procedure-specific direct feedback on opioid prescribing and consumption for their patients who had surgery during days 1-60.

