After this intervention, we will assess pre-post change in opioid prescription size (measured in oral morphine equivalents) from baseline between the two groups for surgeries performed during days 108-167. That is, mean size of post-intervention prescriptions (from electronic medical record queries) will be compared with mean pre-intervention prescription size by the same surgeon for the same procedure in order to calculate change from baseline. Primary outcomes are measures of study feasibility and acceptability given that this is a pilot study. The main exploratory outcome will be mean percentage change in procedure-specific prescription size. We will then compare mean per-surgeon percentage change in prescription size between the direct feedback and no-direct-feedback groups. Multiple regression analyses adjusting for case type and surgical specialty will also be employed to permit more granular examination of the targeted changes. To evaluate other exploratory outcomes, we will contact patients undergoing post-intervention surgeries (during days 108-167) 14 days postoperatively (days 122-181) to assess pre-post changes in patient opioid consumption, satisfaction with analgesia, medical visits for pain, opioid refills, and opioid misuse. We again anticipate contacting 5 patients per day for a total of 300 patients in this second phase.

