Study *patient* candidates will be identified through VUMC EMR queries of performed surgical cases for study surgeon participants. All patient candidates including procedures by study surgeons will be sent a pre-recruitment letter by the VUMC Department of Anesthesiology informing them that may be contacted by telephone postoperatively regarding the study. Study team members contacting patients will be blinded to the surgeon randomization assignments. All patient candidates undergoing included procedures by study surgeons and otherwise meeting inclusion/exclusion criteria will be contacted 14 days postoperatively by telephone or electronic messaging and asked to complete an opioid pill count and a brief verbal questionnaire relating to postoperative opioid use and analgesia. Because preoperative or immediate postoperative consenting for the study might affect patient participants' subsequent opioid consumption, we plan to obtain electronic informed consent from *patients* at the time of contact. Study research coordinators will securely document the consent process. Study personnel will also maintain a screening log containing records for all evaluated candidates as well as reasons for study ineligibility and non-participation of eligible candidates.

Additionally, at the request of the study Data and Safety Monitoring Board, a third participant population will comprise *all* patients undergoing surgery *of any kind* by

surgeons in the nudge intervention group for 60 days following receipt of the nudge intervention. This will entail only EHR queries on POD #10 and #30 (on a rolling basis) for pain-related medical concerns and healthcare visits. This is to determine whether surgeon prescribing practices changed sufficiently following nudge relief to compromise postoperative analgesia and potentially harm patients. These patients will not be contacted by study staff unless they otherwise meet inclusion criteria for the study as listed above.

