## 7 STUDY INTERVENTIONS

### 7.1 Interventions, Administration, and Duration

The one-time contact of *patient* participants will take place on postoperative day 14 (or no later than postoperative day 19) for the initial contact group. After verifying eligibility and documenting consent, patients will be asked to obtain their prescribed opioid pill bottle and conduct a pill count. If the patient consumed the entirety of the prescription and disposed of the bottle, this will be documented. If the patient does not have their pill bottle readily available, arrangements will be made to follow up with the patient by telephone or secure electronic messaging later to complete this aspect of the query. Patient participants will also be asked to answer several questions related to our exploratory outcomes:

- Overall satisfaction with postoperative analgesia (numeric rating scale)
- To select from the following answers: “I received a) too many opioid pills, b) the right amount of opioid pills, c) too few opioid pills.”
- Whether patient required any medical visits primarily due to postoperative pain (office visits, emergency department visits, or hospital admissions)
- Whether additional opioid refills were prescribed after the initial postoperative prescription (this will also be evaluated through EMR queries)
- Evidence of opioid misuse (Current Opioid Misuse Measure-9 [COMM-9])

The one-time intervention for *surgeon* participants in the Intervention Arm will take place on approximately study day 97. This will entail procedure-specific direct feedback (through electronic communication) on patients’ opioid consumption-to-prescription ratio. E.g., “Your abdominal hysterectomy patients were prescribed a mean 60 opioid pills last month. These patients consumed a mean 20 pills (33%).” Surgeon participants who perform more than one of the specified procedures (see section 4.2, above) will receive nudging communications for each individual procedure. Since the data on opioid consumption provided to surgeons is based on self-report data from consented patients, surgeons will be specifically informed that the data is self-reported through inclusion of the following statement: “This is based off self-reported pill counts. The information is self-reported and not validated so it could be erroneous.”

Surgeon participants randomized to the Control Arm will not be contacted directly at any time during the study.

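### Prescribing is measured on the initial prescription and refills as a count with no stated window, so the plan cannot say how far total opioid prescribed changed

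*Combined protocol and SAP*

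**What the plan says.** Section 11.4.2 lists first "Mean pre-post percentage change in procedure-specific prescription size, as measured by OMEs", comparing the same surgeon and procedure before and after the nudge. Section 5 calls this the main exploratory outcome, and Section 11.5 repeats it. None of these places says in its definition which prescriptions count. The nearest answer is the data extraction described in Section 5: "The electronic medical record will be also queried for the size of the initial postoperative opioid prescription as well as evidence of any refills". Size is therefore taken from the initial prescription, and for refills only their presence is mentioned.

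Refills are a separate outcome in Section 11.4.2: "Pre-post change in number of subsequent opioid refills after the initial postoperative prescription (from EMR/PDMP data"). The unit is a number, the source is EMR/PDMP data, and no period is given.

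The only time point attached to refills is the patient contact. Section 5 says second-phase patients are contacted "14 days postoperatively (days 122-181) to assess pre-post changes in patient opioid consumption, satisfaction with analgesia, medical visits for pain, opioid refills" and opioid misuse. Section 7.1 has the patient asked "Whether additional opioid refills were prescribed after the initial postoperative prescription (this will also be evaluated through EMR queries"), and says the contact "will take place on postoperative day 14 (or no later than postoperative day 19) for the initial contact group".

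Section 11.4.2 also lists patient opioid consumption in OMEs. It rests on a count of the prescribed bottle (Sections 8.2.2 and 8.2.4, Pill Count).

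**The concern.** A surgeon who is shown that patients use a fraction of what is prescribed may write a smaller first prescription. Some patients may then receive a refill they would not otherwise have had. In that case the fall in the first prescription is larger than the fall in opioid supplied.

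The distinction matters for this study. Section 4.1 rests the rationale on prescribed opioid that goes unconsumed and becomes available for diversion, which is a question about supply. Section 11.1 says the team chiefly wants precise estimates of mean and variance for planning a larger trial. If the estimate carried forward describes only the first prescription, a planner cannot convert it into an effect on supply.

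The missing refill window is a second gap. Without one, patients in the two phases could be followed for different lengths of time, and the pre-post change in refill number would partly reflect follow-up time.

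**Working it through.** **The plan's own figures.** These reproduce. Five patients a day over 60 days gives 5 × 60 = 300 per phase. Surgery day plus 14 gives 1 + 14 = 15 to 60 + 14 = 74 for the first phase, and 108 + 14 = 122 to 167 + 14 = 181 for the second. Allowing contact up to postoperative day (POD) 19 in the initial group moves its last contact to 60 + 19 = day 79. The documents give no refill rate, refill size or expected change in prescription size, so the rest is illustration.

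**Inputs, all assumed.**
- Initial prescription before the nudge: 60 pills. This is the figure in the example message in Section 7.1, not trial data.
- Initial prescription after the nudge: 30 pills.
- Refills before the nudge: none.
- Refills after the nudge: a share f of patients gets one refill of s pills.

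**Formulas.**
- Change in initial size = 30/60 − 1 = −50%, whatever f and s are.
- Change in total prescribed = (30 + f × s)/60 − 1.

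**Varying the refill share, with s = 30.**

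| f | Change in initial size | Change in refills per patient | Change in total |
|---|---|---|---|
| 0 | −50% | 0 | 30/60 − 1 = −50% |
| 0.10 | −50% | +0.10 | 33/60 − 1 = −45% |
| 0.20 | −50% | +0.20 | 36/60 − 1 = −40% |
| 0.40 | −50% | +0.40 | 42/60 − 1 = −30% |
| 1 | −50% | +1.00 | 60/60 − 1 = 0% |

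**Same refill count, different refill size (f = 0.5).**

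| s (pills) | Change in total |
|---|---|
| 5 | 32.5/60 − 1 = −45.8% |
| 10 | 35/60 − 1 = −41.7% |
| 20 | 40/60 − 1 = −33.3% |
| 30 | 45/60 − 1 = −25% |
| 60 | 60/60 − 1 = 0% |

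Both planned outcomes are identical in every row of the second table (−50% and +0.5 refills per patient), while the total ranges from −45.8% to 0%. The count shows that supply has shifted but not by how much.

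**Sensitivity to the baseline assumption.** If 10% of patients already had a 30-pill refill before the nudge, the baseline total is 60 + 0.1 × 30 = 63. With a further 10% refilling afterwards, the post-nudge total is 30 + 0.2 × 30 = 36, and the change is 36/63 − 1 = −42.9%, in place of −45%.

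**Whether another planned measure fills the gap.**
- Consumption in OMEs is a partial check. The pill count concerns the prescribed bottle, and a finished and discarded bottle counts as 0 remaining. No rule says how pills from a refill enter the calculation.
- The safety look-up in Section 6.3 ("This will entail only EHR queries on POD #10 and #30 (on a rolling basis")) covers only patients of intervention-arm surgeons and looks for pain-related concerns and visits. It does not collect OMEs.

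**The case against.** The strongest reply is that the split would be visible. Initial size and refill number are separate outcomes, and a fall in one beside a rise in the other is what alerts a reader to substitution. That stands. A reader might infer that the plan hides the shift, or that it overstates both benefit and harm. The documents do not support this. Both results would be true, Sections 11.4.2 and 11.5 never present prescription size as total supply, and refill requests are an objective in their own right (Sections 1.2 and 3.2). What remains is that the size of the net change cannot be recovered.

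A reader might also infer that refills are counted only to day 14, so that a smaller first prescription brings refills inside the window in the nudged arm and leaves them outside it in the control arm. The refill outcome states no day. Day 14, or up to POD 19 in the initial group, is the patient contact. A 14-day reading is possible from Section 5, but refill timing is not an outcome and nothing in the plan establishes differential capture. The supportable defect is an unspecified window.

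A third reply is that the protocol expects large unused supply. Section 4.1 cites up to 70% unconsumed, and the message in Section 7.1 has 20 of 60 pills used. For such a patient 30 pills still exceed use, no refill is needed, and −50% is the true change in total. This is the f = 0 row, and it may be the commonest case. Section 11.1 itself hypothesises no difference between arms in refills. The illustration therefore bounds what could happen and does not predict it.

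Finally, these are exploratory outcomes in a pilot, and the mean and variance of initial prescription size remain valid planning inputs for that endpoint. That also stands, and it limits the weight of the point.

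**Conclusion.** The point holds in a limited form. Read with Section 5, the prescribing outcome captures the initial prescription only, refills are a count without a window, and no outcome combines them in OMEs. The plan can show that prescriptions became smaller and refills more frequent, but not how far total opioid prescribed changed. Under the assumed 60-to-30 cut with 30-pill refills in 10% to 40% of patients, the gap between the fall in initial size and the fall in total is 5 to 20 percentage points. It is zero if no one needs a refill.

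The conclusion rests on reading prescription size as the initial prescription, since the outcome definition does not repeat that word. If refills were meant to be included, the definition would still need to say so and give a period. The consequence is confined to the exploratory prescribing objective and the planning estimates. No primary conclusion depends on it.

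**What to change.** In Sections 11.4.2 and 11.5:

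1. State that prescription size means the initial postoperative prescription.
2. Count refills over one fixed window, the same in both arms and both phases, for example POD 0 to 30, and give the reason for the length chosen. Any window misses later refills, but a common one makes the comparison fair.
3. Beside initial size, report as a supportive exploratory outcome the total OMEs prescribed per patient (initial plus refills) over that window, summarised by surgeon and procedure in the same way.
4. Use one patient population definition in both phases for these outcomes. At present Section 8.2.2 takes baseline prescribing from patients who completed screening, consent and pill count, whereas Section 8.2.4 takes post-intervention prescribing from all who completed screening.

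**Cost.** EMR/PDMP is already the refill source and no extra patient contact is needed, but refill quantities must be extracted as well as their number. With a 30-day window, the first-phase look-up ends on day 60 + 30 = 90, before the nudge at about day 97. The second-phase look-up ends on day 167 + 30 = 197. The POD 30 queries in Section 6.3 already imply work to about day 97 + 60 + 30 = 187, so the extension is roughly 10 days. Those queries would not supply the data as they stand, because they omit control-arm patients and do not record OMEs.

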## 11.5 Data Analyses

Primary feasibility and acceptability outcomes will be assessed on a descriptive basis among both the intervention and control surgeon groups (each group will be given a full explanation of the nature of the study following completion). After the intervention, we will also assess pre-post change in opioid prescription size (measured in oral morphine

equivalents) between the two groups. We will compare postoperative prescription size from the baseline (surgeries performed during days 1-60) to prescription size for surgeries performed during days 108-167. The specific exploratory outcome will be mean percentage change in procedure-specific prescription size. That is, mean size of post-intervention prescriptions (from electronic medical record queries) will be compared with mean pre-intervention prescription size by the same surgeon for the same procedure in order to calculate change from baseline. We will then compare mean per-surgeon percentage change in prescription size between the Intervention and Control Arms. We will plan a multiple regression analysis adjusting for case type and surgical specialty to further explore the targeted intervention effects.

To evaluate our other exploratory outcomes, we will assess pre-post changes across groups in patient opioid consumption, satisfaction with analgesia, medical visits for pain, opioid refills, and opioid misuse.

Additionally, we will examine differential consent rates between patients in the follow-up intervention patient group vs. those in the follow-up control patient group using descriptive statistics. This is due to the potential for varying consent rates among patients who are more or less satisfied with their postoperative analgesia following delivery of the one-time study intervention to surgeons.

We will not undersample or oversample surgeons who are women and/or members of minority racial and ethnic groups, so we expect to enroll them in proportion to their population prevalence at VUMC. We will use VUMC EMR data to assess sex/gender and race/ethnicity of patient participants, and will conduct analyses to investigate any differences between groups (including any sex/gender or race/ethnicity differences in willingness to participate in the study).

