### 1.2 Objectives

Overall goal: Develop pilot data for a new, easily scalable strategy to optimize post-surgical opioid prescribing.

Specific objective #1: Evaluate feasibility and acceptability of carrying out a novel nudge intervention that may reduce excess postoperative opioid prescribing by surgeons.

Exploratory objective #2: Determine whether the nudge intervention leads to changes in subsequent postoperative opioid prescribing by surgeons.

Exploratory objective #3: Determine whether this technique affects patient opioid consumption, refill requests, medical visits for pain, satisfaction with analgesia, and opioid misuse.

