#### **4.2 Study Rationale**

Evidence-based postoperative prescribing guidelines have been propagated(7-10) in order to decrease both the number of surgical patients developing new persistent opioid use and the overprescribing of post-surgical opioids. Other nudging techniques like changing electronic medical record prescription size defaults have been used in the surgical setting to decrease opioid prescribing,(11) although such tactics run the risk of increasing opioid prescribing for already-low prescribers.(12)

Despite these initiatives, evidence remains limited regarding the optimal methods for reducing post-surgical opioid prescribing.(13) Our proposed project will test a novel nudging technique that has not been studied in the postoperative opioid prescribing space: direct feedback to surgeons about their patients' opioid prescription-to-consumption ratios. Direct feedback to opioid prescribers after patients suffered a fatal opioid overdose has been shown to reduce subsequent opioid prescribing significantly.(14) We believe that providing granular data to a wide population of surgical prescribers (not just those whose patients overdose) will prove similarly effective. Should our intervention decrease

surgical prescribing, we anticipate it playing a significant role in the national strategy to combat the opioid crisis.

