## 11 STATISTICAL CONSIDERATIONS

### 11.1 General Design Issues

This is a pilot randomized controlled trial assessing the effect of a brief behavioral nudging intervention on surgeons' postoperative opioid prescribing. In addition to determining feasibility and acceptability, we are chiefly interested in obtaining precise estimates of mean and variance to aid in planning a larger, sufficiently powered efficacy trial.

Exploratory hypotheses include that (1) surgeons in the Intervention Arm will exhibit a larger pre-post percentage change in procedure-specific prescription size (measured by oral morphine equivalents [OMEs]) compared with surgeons in the Control Arm who do not receive the nudging intervention and (2) there will be no pre-post difference between the Intervention and Control Arms in terms of patient opioid consumption, opioid refills, medical visits for pain, satisfaction with analgesia, and opioid misuse.

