#### 11.2.1 Treatment Assignment Procedures

For randomization, a list of all surgeon participants will be generated. Using random.org's sequence generator, a true random integer sequence derived from atmospheric noise will determine order in the list. Randomization will be stratified by surgical specialty (e.g., neurological surgery) and by mean opioid prescribing amount during the first 60-day surgical period prior to randomization (greater or equal to median vs. below median). We will at minimum ensure an even or near-even split among the four overall major surgical divisions (general, orthopedic, gynecologic, and neurological) across the intervention and control arms.

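### The prescribing analyses estimate one average arm effect and omit the baseline-prescribing stratum used for randomization, so effects that differ by stratum would be attenuated and not reported

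*Combined protocol and SAP*

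**What the plan says.** All references are to the combined protocol and SAP.

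- **Question.** Exploratory objective #2 in 1.2 is: "Determine whether the nudge intervention leads to changes in subsequent postoperative opioid prescribing by surgeons". The hypothesis in 11.1 is that "surgeons in the Intervention Arm will exhibit a larger pre-post percentage change in procedure-specific prescription size" than controls; it gives no direction.
- **Outcome.** Section 11.4.2 lists "Mean pre-post percentage change in procedure-specific prescription size, as measured by OMEs", computed for the same surgeon and procedure.
- **Comparison.** Section 11.5 states: "We will then compare mean per-surgeon percentage change in prescription size between the Intervention and Control Arms". Section 5 describes the same comparison.
- **Regression.** Section 11.5 adds: "We will plan a multiple regression analysis adjusting for case type and surgical specialty to further explore the targeted intervention effects". Section 5 presents this as the finer-grained look. Neither section names baseline prescribing or an interaction with arm.
- **Stratum.** Section 11.2.1 stratifies randomization by specialty and by "mean opioid prescribing amount during the first 60-day surgical period prior to randomization (greater or equal to median vs. below median"). The stratum is not mentioned again in the analysis plan.
- **Rationale.** Section 4.2 says of changed prescription-size defaults in the electronic record that "such tactics run the risk of increasing opioid prescribing for already-low prescribers".
- **Purpose.** Section 11.1 says that, beyond feasibility and acceptability, the pilot is mainly meant to supply mean and variance estimates for planning an efficacy trial.

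**The concern.** An average of signed changes measures net shift. It cannot separate a nudge that changes nobody from one that lowers prescribing in one group and raises it in another. Adjusting for case type and specialty does not alter this, because the model still has one arm coefficient. Adding baseline prescribing only as a covariate would not alter it either.

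The protocol gives a reason to look at baseline level: it treats increases among low prescribers as a known weakness of another nudge, and it randomizes within high and low prescribing strata. The analysis then makes no use of those strata.

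What is at stake is the planning information. If effects differ in direction by stratum, the estimated mean is diluted and the intervention-arm variance is inflated. Both would be passed to the larger trial with no planned result to explain why.

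**Working it through.** **Inputs from the documents.** Section 11.2 expects up to 60 surgeons. At 1:1 that is 60/2 = 30 per group, which reproduces the stated figure and exceeds the 12-per-group rule of thumb. A median split gives at most about 30/2 = 15 surgeons per arm per stratum.

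**Assumed, because the documents give none.** Two-sided 5% level; within-stratum SD of per-surgeon percentage change of 25, 30 or 40 points; true effects as listed below; net control change of zero in each stratum. A regression-to-the-mean shift common to both arms drops out of the between-arm contrasts used here.

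**Step 1: what the mean comparison estimates.** Mean difference = (effect in high stratum + effect in low stratum)/2.
- -20/+20: (-20 + 20)/2 = 0
- -30/+15: (-30 + 15)/2 = -7.5
- -20/+10: (-20 + 10)/2 = -5
- -20/-20: -20

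Only the equal and opposite case cancels. The other two opposite patterns shrink.

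**Step 2: intervention-arm SD.** SD_int = sqrt(SD² + (half the gap between strata)²). For -20/+20 the half-gap is 20:
- SD 25: sqrt(625 + 400) = 32.0
- SD 30: sqrt(900 + 400) = 36.1
- SD 40: sqrt(1600 + 400) = 44.7

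**Step 3: arm-by-stratum term.** The contrast is the arm difference in the high stratum minus that in the low stratum, so four cell means of 15 each. SE = SD × sqrt(4/15) = 12.9, 15.5 and 20.7. For -20/+20 the contrast is 40 points; detection uses the noncentral t with 56 df.

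**Step 4: detection rates.** The mean comparison is a two-sample t-test, simulated 20,000 times per scenario. Example for -20/+10 at SD 30: SD_int = sqrt(900 + 225) = 33.5, SE = sqrt((1125 + 900)/30) = 8.2, and 5/8.2 = 0.61 standard errors.

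| True effect high/low | Mean comparison, SD 25 / 30 / 40 | Arm-by-stratum term, SD 25 / 30 / 40 |
|---|---|---|
| -20/+20 | 2.5% / 3.0% / 3.8% | 86.1% / 71.8% / 47.7% |
| -30/+15 | 12% / 10% / 8% | 92.9% / 81.5% / 57.2% |
| -20/+10 | 9% / 8% / 6% | 62.7% / 47.7% / 29.8% |
| -20/-20 | 86% / 72% / 48% | 5% (no interaction) |

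In the first row the mean comparison falls below 5% because the gap between strata inflates the SD it uses. The last row is why the mean comparison should stay: it works well when the effect is uniform.

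**Step 5: precision within a stratum.** Half-width = 1.96 × SD × sqrt(2/15) = 17.9, 21.5 and 28.6 points at SD 25, 30 and 40.

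**Step 6: how fragile Step 4 is** (-20/+20, SD 30).
- 20 surgeons per arm: SE = 30 × sqrt(4/10) = 19.0, and detection falls from 72% to about 54%.
- If 4 of 15 surgeons in each intervention cell respond opposite to their stratum (an assumption), the cell means become (11 × -20 + 4 × 20)/15 = -9.3 and +9.3. The contrast is 18.7 and detection is about 17%.

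**The case against.** The case against has real force.

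- **Exploratory outcome in a feasibility pilot.** This stands. The primary outcomes in 11.4.1 are untouched, and 11.5 names no test or significance level. The rates above are only a yardstick for how visible a pattern would be.
- **The cited risk belongs to another intervention.** This stands. Section 4.2 speaks of record defaults. A reader might infer that this nudge raises prescribing among low prescribers. No section says so. It is conceivable, since a surgeon whose patients took nearly every pill would see a ratio near 100%. But 4.1 says up to 70% of pills go unused and the sample message in 7.1 shows 33% consumed, so much of the feedback may point downward.
- **The stratum is an imperfect marker.** This stands. Feedback is a consumption ratio, while the stratum is an amount. Section 11.2.1 does not say whether the median is taken overall or within specialty. If overall, the stratum partly reflects case mix. That section also guarantees, as a minimum, only near balance across the four surgical divisions.
- **A net reduction is a natural target.** This stands in part. Sections 1.2 (objective #1) and 3.1 speak of reducing excess prescribing, which is why the overall comparison should be kept. It does not answer whether the effect is the same across strata.
- **The split could be made later.** A reader might infer that the trial could never show a differential effect. That goes too far: the per-surgeon data and strata will exist, and an inflated intervention-arm SD would be a hint. But an unplanned look at change within the intervention arm would mislead, because regression to the mean pulls high prescribers down and low prescribers up in both arms. That favours naming the between-arm contrast in advance.

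**Conclusion.** The point holds as a low-cost improvement to an exploratory analysis. Every planned prescribing analysis yields one average signed effect, and the baseline stratum used for randomization enters none of them. If effects differ in direction by stratum, the mean is attenuated and the variance inflated, and nothing planned would reveal it.

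A reader might infer that opposite effects would simply cancel and the trial would report no change. That is true only for equal and opposite effects in equal-sized strata. At -30/+15 or -20/+10 a difference of -7.5 or -5 points remains.

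The detection rates for the arm-by-stratum term are a best case. They rest on assumed effects and SDs, a full 30 surgeons per arm, even strata, and every surgeon responding as the stratum predicts. The documents also do not support calling any rise in the below-median stratum harmful; that is a clinical judgement they do not make.

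**What to change.** In 11.5:

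1. Keep the overall comparison of mean per-surgeon percentage change.
2. Add the randomization stratum ("greater or equal to median vs. below median") to the planned regression, beside case type and specialty, with an exploratory arm-by-stratum term.
3. Report the between-arm difference in percentage change with 95% CIs, overall and within each stratum. Base stratum results on this contrast, not on change within an arm.
4. Label the stratum results exploratory and imprecise: at most about 15 surgeons per arm per stratum, with a half-width of roughly 18 to 22 points at an SD of 25 to 30, wider with a larger SD or fewer surgeons. Report the direction of change without labelling it clinically.

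It would also help to state in 11.2.1 whether the median is taken across all surgeons or within specialty, so that the analysis stratum is the one used to randomize.

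The cost is a few sentences and two model terms (stratum and its interaction with arm). No new data, participants or contacts are needed.
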